2.5.4 Windows for time points

The following process will be applied for visit re-allocation. Re-allocated visits will be used in all statistical analyses (descriptive statistics, plots, and statistical models).

No re-allocation will be performed for nominal visits already provided in the clinical database (Visit 1 to Visit 20).

SMPG

In the clinical database, SMPG profiles transferred from the e-diary will not be assigned to a protocol visit. For the analysis, they will be assigned to the next visit actually performed by the patient after the date/time of data collection (Visit 3 to Visit 12, or Visit 700).

In the clinical database, SMPG assessments which do not correspond to a 7-point profile transferred from the e-diary will not be assigned to a protocol visit. For the analysis, they will be assigned to the next visit after the date/time of data collection.

Insulin doses

In the clinical database, insulin doses transferred from the e-diary will not be assigned to a protocol visit. For the analysis, they will be assigned to the next on-site visit actually performed by the patient after the date/time of data collection.

PROs and ClinRO

In the clinical database, PROs and ClinRO transferred from the e-diary will not be assigned to a protocol visit. For the analysis, they will be assigned to the video chat/phone call/ on-site visit using the date/time of data collection and the date of first IMP taken (or Randomization date if no IMP taken) as reference for derivation of the Study day .

Table 2 - Reallocation time windows definition

Scheduled visit post baseline	Targeted study day	Analysis window in study days
DTSQs, DDS, HFS-II, WPAI-SP, OSES Part 1		
Day 1 (Visit 2 Step 2)	1	-28 to 1
Week 24 (Visit 12)	169	141 to 196
DTSQc, WIWI, OSES Part 2, OSEP Part 2		
Week 24 (Visit 12)	169	141 to 196
OSES Part 1		
Day 1 (Visit 2 Step 2)	1	-28 to 1
Week 1 (Visit 3)	8	5 to 11
Week 2 (Visit 4)	15	12 to 18
Week 3 (Visit 5)	22	19 to 25
Week 4 (Visit 6)	29	26 to 32
Week 6 (Visit 7)	43	36 to 49
Week 8 (Visit 8)	57	50 to 63
Week 12 (Visit 9)	85	71 to 98
Week 16 (Visit 10)	113	99 to 126
Week 20 (Visit 11)	141	127 to 154
Week 24 (Visit 12)	169	155 to 196

Scheduled visit post baseline	Targeted study day	Analysis window in study days
RUQ		
Day 1 (Visit 2 Step 2)	1	-28 to 1
Week 4 (Visit 6)	29	15 to 42
Week 8 (Visit 8)	57	43 to 70
Week 12 (Visit 9)	85	71 to 98
Week 16 (Visit 10)	113	99 to 126
Week 20 (Visit 11)	141	127 to 154
Week 24 (Visit 12)	169	155 to 196

Study days are calculated from the day of first IMP, the day of first IMP injection being Day 1. For randomized but not treated patients, Day 1 is the day of randomization.

End of treatment visit

The following analysis windows will be applicable to re-allocate the premature end of treatment assessments (premature EOT visit) for HbA1c and FPG assessments.

Table 3 - Reallocation time windows definition

Scheduled visit post baseline	Targeted study day	Analysis window in study days
HbA1c and FPG		
Week 16 (Visit 10)	113	85 to 140
Week 24 (Visit 12)	169	141 to 196

Study days are calculated from the day of first IMP, the day of first IMP injection being Day 1. For randomized but not treated patients, Day 1 is the day of randomization.

Study days are calculated from the day of first IMP injection; the day of first IMP injection being Day1.

To retrieve all safety and other assessments performed at the end of treatment visit, the following process will be followed: if a patient discontinues the treatment prematurely, end of treatment assessments will be re-allocated to the next scheduled visit for the patient. The next scheduled visit for each patient will be determined as the next visit that should be performed as per protocol, following the last visit actually performed by the patient before end of treatment visit.

For a given parameter, the value will not be re-allocated in the following cases:

- If the parameter is not planned to be collected at the re-allocation visit.
- If a value is already available for the parameter at the re-allocation visit.

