Self-monitoring of plasma glucose readings will be used to guide the basal and mealtime insulin titration to reach glucose targets. The investigators should review the SMPG records at each onsite visit and also ask the pattern of fasting and postprandial SMPG at the phone visits so that they can provide instruction to the patients for appropriate insulin dose adjustment. Investigators may request more frequent blood glucose test and/or at specific time, eg, midnight, if needed, to help the patients optimize insulin dosage.

The performance of SMPG is outlined in [Table 5](#) and also specified also in [Section 1.2](#) flow chart.

Table 5 – Instruction for SMPG performed during the study

SMPG	Definition	Frequency	
		Recommended	Mandatory
5-points	Before breakfast, lunch, and dinner, 2 hours post a main meal (or as per investigator's instruction) and at bedtime	5 days per week	3 days during the week prior to each visit
7-points	before and 2 hours after breakfast, lunch, and dinner, and at bedtime	As needed	1 day during Week -1, 15, and 23

SMPG: self-monitoring of plasma glucose

5-point SMPG profiles

Patients should measure a 5-point SMPG profile (before breakfast, lunch, and dinner [before insulin injection when applicable], 2 hours after the patient's main meal [eg, lunch or dinner] or as per investigator's instruction, and at bed time) for at least 3 days per week before each visit.

Before breakfast, SMPG should be measured after the patient wakes up, before breakfast, and before injection of any insulin (if applicable). Preferably, no food should have been taken overnight. The values will be used as fasting SMPG to guide the modification in insulin dose ([Section 8.1.6](#)).

7-point SMPG profiles

Seven-point blood glucose profiles should be measured at the following 7 time-points: before (preinjection after randomization) and 2 hours after breakfast; before and 2 hours after lunch; before and 2 hours after dinner; and at bedtime). Two hours post meal is defined as 2 hours after the start of the meal.

Patients are required to have 7-point SMPG profiles performed on at least 1 day in the week before the baseline visit and before the visits of Week 16 and Week 24 (EOT).

SMPG during episodes of symptomatic hypoglycemia

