2.4.4.2 Analyses of secondary efficacy endpoints

Secondary efficacy endpoints are described in [Section 2.1.4](#).

All secondary efficacy endpoints will be analyzed or summarized on the 24-week randomized period (to assess the ITT estimand) using the ITT population.

The following secondary efficacy endpoints will be analyzed using the same model (same analysis) as the one used for primary endpoint (MMRM model) as described in [Section 2.4.4.1.1](#).

- HbA1c (%): change from baseline to Week 16;

The following secondary efficacy endpoints will be analyzed using the same approach as the one used for primary endpoint (MMRM model) as described in [Section 2.4.4.1.1](#). The model will include fixed categorical effects of study conduct approach group, visit, study conduct approach-by-visit interaction, randomization stratum of site, randomization stratum of HbA1c (<7.6 % and ≥ 7.6%), the continuous fixed covariates of the corresponding baseline value, and baseline value-by-visit interaction.

- FPG: change from baseline to Week 16 and Week 24;
- Change in mean 24-hour plasma glucose based on 7-point SMPG from baseline to Week 16 and Week 24;

For the model on change in FPG and on the mean 24-hour plasma glucose based on 7-point SMPG, the visit term has 2 levels (Week 16 and Week 24).

No formal comparison and no p-value will be provided.

The following secondary endpoints will be analyzed using descriptive measures:

- Change in 7-point SMPG profiles per time-point from baseline to Week 16 and Week 24;

For all continuous endpoints, observed values and change from baseline will be also described for all visits with mean, median, SD, minimum and maximum. A figure representing the mean (+/- SE) change from baseline at each visit will be produced by study conduct approach group.

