Handling of potentially clinically significant abnormalities

If a patient has a missing baseline he will be grouped in the category “normal/missing at baseline.”

For PCSAs with 2 conditions, one based on a change from baseline value or a normal range and the other on a threshold value, with the first condition being missing, the PCSA will be based only on the second condition.

For a PCSA defined on a threshold and/or a normal range, this PCSA will be derived using this threshold if the normal range is missing.

Measurements flagged as invalid by the laboratory will not be summarized or taken into account in the computation of PCSA values.

Handling of hypoglycemia event classification when some classification items are missing

Rule for handling missing data in classification items for hypoglycemia event will be provided in ADaM metadata.

Handling of missing data in the calculation of 7-point SMPG variables

For a given 7-point SMPG profile, at least 4 available measurements in the last 7 days are required to be taken into account in the statistical analyses (including the descriptive analyses at each time-point).

Handling of missing data in the calculation of average pre-breakfast SMPG,

At least 3 pre-breakfast (fasting) SMPG values in the last 7 days are required to be taken into account in the statistical analyses (including descriptive analyses at each time-point).

Handling of missing data in the calculation of insulin doses

At each visit, the average daily insulin doses (basal, mealtime, and total) will be calculated as the average of the daily insulin doses available in the week (7 days) before the visit.

No minimum number of available doses will be required.

For insulin doses in U/kg, if the body weight measurement is missing at a given visit, the last available measurement from previous visit will be used.

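### A 7-point SMPG profile recorded on time before a missed Visit 10 is carried to Week 20 or Week 24, because SAP 2.5.4 assigns profiles by the next visit performed and not by date

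*SAP*

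**What the plan says.** - **When the profile is due.** Protocol 9.2.2.2 asks for at least one day of 7-point profile "in the week before the baseline visit and before the visits of Week 16 and Week 24 (EOT". Table 5 of the protocol and note i of the flow chart agree.
- **How it is assigned.** SAP 2.5.4 says of e-diary profiles that "they will be assigned to the next visit actually performed by the patient after the date/time of data collection". The eligible visits are "Visit 3 to Visit 12, or Visit 700". Visit 11, which is Week 20, is therefore eligible. The SAP does not define Visit 700.
- **Where it is analysed.** SAP 2.4.4.2 models mean 24-hour glucose from the 7-point profile, and there "the visit term has 2 levels (Week 16 and Week 24". Values per time-point are described at the same two weeks.
- **Completeness.** SAP 2.5.3 says that for a given profile "at least 4 available measurements in the last 7 days are required to be taken into account in the statistical analyses". It does not say from which date the 7 days count back. SAP 2.5.2 gives the same minimum of 4 points with no 7-day limit.
- **Day windows elsewhere.** SAP Table 2 gives study-day windows for questionnaires only. The Table 3 windows "will be applicable to re-allocate the premature end of treatment assessments (premature EOT visit) for HbA1c and FPG assessments", and SAP 2.5.5 extends them to unscheduled central-laboratory HbA1c and FPG. SAP 2.4 says that all analyses use visits defined by the windows in 2.5.4, but none is given for SMPG.

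**The concern.** A glucose profile carries its own date and time. Under the SAP rule, its week label depends instead on which visit the patient happens to attend next. If the visit it was meant for does not take place, a correctly timed value is removed from the week it describes.

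This does not fit the stated aim of the analysis. SAP 2.4.4.2 uses the 24-week randomized period for secondary endpoints, and Protocol 11.4.3.2 uses all available post-baseline data. It also treats dated data unevenly: a resource-use questionnaire completed on Day 110 counts as Week 16 under Table 2, whereas a 7-point profile from the same day need not. At stake is a missing Week 16 value and, with two missed visits, an old value shown under Week 24.

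**Working it through.** **Inputs.** Target study days for Weeks 16, 20 and 24 are 113, 141 and 169 (SAP Tables 2 and 3). Visit windows are ±4 days for Visit 10 and ±3 days for Visits 11 and 12 (protocol flow chart). Day 110 is an assumed example of a profile recorded in the week before a Visit 10 planned for Day 113, that is, on Days 106 to 112.

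**1. Reproduce the target days.** Target day = 7 × week + 1: 7 × 16 + 1 = 113; 7 × 20 + 1 = 141; 7 × 24 + 1 = 169. These match the SAP.

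**2. Apply the rule to a Day 110 profile, with attended visits on target.**

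| Visits attended | Assigned to | Label | Gap to that visit |
|---|---|---|---|
| Visit 10 | Visit 10 | Week 16 | 113 − 110 = 3 days |
| Visit 10 missed, Visit 11 attended | Visit 11 | Week 20 | 141 − 110 = 31 days |
| Visits 10 and 11 missed, Visit 12 attended | Visit 12 | Week 24 | 169 − 110 = 59 days |

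**3. Allow for the visit windows.** For profiles on Days 106 to 112, the gap to Visit 11 (Days 138 to 144) runs from 138 − 112 = 26 to 144 − 106 = 38 days. The gap to Visit 12 (Days 166 to 172) runs from 166 − 112 = 54 to 172 − 106 = 66 days.

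**4. Apply the 7-day rule.** All these gaps exceed 7 days. If the 7 days count back from the assigned visit, the profile is dropped altogether. If they do not, it stays under the wrong week. In neither reading does it return to Week 16.

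**5. Look for another rule that would rescue it.**
- Table 2, Table 3 and SAP 2.5.5 do not cover SMPG, as set out above.
- SAP 2.5.4 moves assessments at a premature end-of-treatment visit to the next scheduled visit. For a patient whose last attended visit was Visit 9, that is Visit 10, so the profile could stay at Week 16. This is the one exception.
- Protocol 10.1.5 postpones the end-of-treatment visit when the 7-point profile is missing or incomplete. For Visit 10, Protocol 10.1.4 provides only a reminder.

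**6. Apply a day window instead.** Under the Table 2 window for Week 16 in the resource-use questionnaire (Days 99 to 126), the Day 110 profile is Week 16 whichever visits are attended.

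**The case against.** The strongest reply is that assigning diary data to the next visit mirrors the design, since the profile is meant to precede the visit. For every patient who attends Visits 10 and 12 as planned, the rule gives the right label. That is correct, and it confines the problem to a missed Visit 10.

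The Week 24 mislabelling is also limited. A patient who reaches Visit 12 should have a fresh profile, because that visit is postponed otherwise. SAP 2.5.5 then prefers the assessment closest to the target day. That sentence follows the HbA1c and FPG windows, however, and the SAP does not say whether it reaches SMPG. Even if it does, the Week 16 value is not restored.

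A reader might infer more than the documents support:

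- **Profiles taken after an attended Visit 10.** These are outside the protocol timing and follow that visit's SMPG and dose review. Week 16 is lost only if no valid profile preceded the visit.
- **Profiles taken after Visit 12.** The randomized period in SAP 2.1.3 ends at Visit 12, and postponement largely covers this case.
- **HbA1c and FPG as generally windowed by day.** They are not. Scheduled samples keep their nominal visit, and the windows apply to premature end-of-treatment and unscheduled samples.
- **No possible display at Week 20.** SAP 2.4.4.2 also describes continuous endpoints at all visits, so a carried-over profile might appear there.

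**Conclusion.** The point holds in one defined case: the profile is recorded on time, Visit 10 is missed, and the next contact is not a premature end-of-treatment visit. A valid value is then lost from Week 16. It is labelled Week 20, or Week 24 if Visit 11 is missed as well, or it is dropped, depending on how the 7-day rule is read.

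The size is small. This is a secondary endpoint, and SAP Section 2 reports early termination with 15 patients randomized, leaving basic descriptive tables or listings in place of the planned model. Each affected patient would be 1/15 = 6.7% of those randomized. The documents do not say how many patients, if any, missed Visit 10, so no loss rate can be given.

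A reader might also infer a bias between the arms, because Visit 10 is on-site in one and virtual in the other. The rule treats both kinds of visit alike, and nothing in the documents shows that missed visits would differ by arm.

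**What to change.** Replace the next-visit rule for 7-point profiles in SAP 2.5.4 with assignment by collection date:

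- **Windows.** Week 16: Days 99 to 126. Week 24: Days 155 to 196, limited to the 24-week randomized period. Both already stand in Table 2 for the resource-use questionnaire and OSES Part 1.
- **Choice of profile.** Give priority to the planned profile in the week before an attended Visit 10 or Visit 12. Otherwise take the one closest to Day 113 or Day 169.
- **Completeness.** Apply the minimum of 4 of 7 points within the profile itself, and remove the unanchored 7-day wording from 2.5.3.

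The Table 3 windows (Days 85 to 140 and 141 to 196) are too wide for this purpose. They take in the target day of Visit 9 (7 × 12 + 1 = 85) as Week 16 and that of Visit 11 (Day 141) as Week 24.

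The cost is SAP wording and derivation code; no new data are needed. The downside is that a retained profile may lie up to 14 days before (113 − 99) or 13 days after (126 − 113) the Week 16 target. For Week 24 it may lie 14 days before (169 − 155), and later only within the randomized period. A profile taken after an attended Visit 10 could also fill Week 16 when none preceded the visit. Showing the collection day in the listing would make both visible.

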2.4.3.2 Daily insulin doses

The process described in [Section 2.5.4](#) will be applied to assign visits to the insulin doses transferred from the e-diary into the clinical database, and to retrieve doses in case of premature treatment discontinuation.

At each visit, the average daily basal, mealtime, and total (basal plus mealtime) insulin doses (U and U/kg body weight) will be calculated as the mean of daily insulin doses collected in the week before the visit. No minimum number of available doses will be required. Technical details related to the computation and handling of missing data are described in [Section 2.5.3](#).

The daily insulin doses (basal, mealtime, total) will be described at each visit, as well as the changes from baseline, relative change from baseline and change from previous visit.

The calculation of daily insulin doses at baseline is defined in [Section 2.1.1](#).

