2.5.5 Unscheduled visits

The analysis windows mentioned in [Section 2.5.4](#) will be applicable to re-allocate the unscheduled assessments (measurements from the central laboratory only) for HbA1c and FPG assessments.

After applying the time windows as mentioned in [Section 2.5.4](#), if two assessments are associated to the same time point, the closest from the targeted study day is used. In case of equality, the earliest measurement is used.

The determination of baseline for HbA1c and FPG variables is based on all measurements from both scheduled and unscheduled visits (measurements from the central laboratory only). The determination of baseline for safety parameters is based on all assessments from both scheduled and unscheduled visits too. The determination of the last on-treatment value for safety parameters is also based on all assessments from both scheduled and unscheduled visits. Measurements from the unscheduled visits (including results from local laboratory when no corresponding central laboratory results are available) are also considered for PCSA summary of safety parameters.

Unscheduled visit measurements are not included in the by-visit summaries.

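### SAP 2.5.4 ties e-diary insulin doses to on-site visits, so the virtual arm has no scheduled post-baseline visit at which its weekly mean dose can be reported

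*SAP*

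**What the plan says.** SAP 2.4.3.2 relies on Section 2.5.4 for visit assignment: that procedure "will be applied to assign visits to the insulin doses transferred from the e-diary into the clinical database". The same sentence gives it a second use, for patients who stop early: "and to retrieve doses in case of premature treatment discontinuation". The dose statistic is the mean of the daily doses from the week before the visit. On reporting: "The daily insulin doses (basal, mealtime, total) will be described at each visit, as well as the changes from baseline". SAP 2.5.3 says the same: "At each visit, the average daily insulin doses (basal, mealtime, and total) will be calculated".

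The assignment rule for e-diary doses in SAP 2.5.4 is that "they will be assigned to the next on-site visit actually performed by the patient after the date/time of data collection". In the same section, SMPG profiles go to the "next visit actually performed by the patient after the date/time of data collection (Visit 3 to Visit 12, or Visit 700"), with no limit on visit mode. PROs and ClinRO go to video, phone or on-site visits, each named.

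On the design, SAP 1.1 and Protocol 6.1 give virtual patients one site attendance, the physical examination before the first IMP dose. Protocol Section 10 counts 5 on-site and 7 telephone visits for the traditional group, and 11 virtual visits plus one mixed visit (Visit 2-Step 2) for the virtual group. Protocol 10.1.4 and 10.1.5 make Visits 6, 8, 10 and 12 virtual for that group.

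**The concern.** The trial compares two ways of running a study, one of which has no site visits after the start of treatment. A derivation keyed to on-site visits therefore works in only one arm. Insulin dose is a secondary endpoint in the protocol (synopsis and 9.2.2.3). Its most informative period is early: Protocol 9.4 expects the optimal dose to be reached within 8 weeks, and 8.1.6 schedules weekly contacts in the first month to decide on dose adjustment. If 2.5.4 is programmed as written, the diary-based dose table has an empty virtual column at every visit, and neither arm has an entry at Visits 3 to 5. Titration under the two approaches could not be compared from that table, although Protocol 9.2.2.3 asks both groups for the diary entries needed.

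**Working it through.** **Inputs.** Visit modes come from the flow chart (Protocol 1.2, SAP Appendix B), the diary schedule from Protocol 9.2.2.3, and the assignment rules from SAP 2.5.4.

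**Step 1: reproduce the protocol's visit counts.** Visit 2-Step 2 and Visits 3 to 13 make 12 visits per arm. Traditional: Visits 2-Step 2, 6, 8, 10 and 12 are on-site (5) and the rest are by phone (7). Virtual: Visit 2-Step 2 is mixed (1) and Visits 3 to 13 are virtual (11). Both match Protocol Section 10.

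**Step 2: apply the rule to the treatment visits.** Visits 3 to 12 are 10 per arm. Visits 3 to 8 (Weeks 1, 2, 3, 4, 6 and 8) are the 6 visits of the titration phase.

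| Visits with a diary-based weekly mean | Virtual | Traditional | Both arms |
|---|---|---|---|
| On-site rule, Visits 3 to 12 | 0 of 10 | 4 of 10 (6, 8, 10, 12) | 0 of 10 |
| On-site rule, Visits 3 to 8 | 0 of 6 | 2 of 6 (6, 8) | 0 of 6 |
| SMPG rule, Visits 3 to 12 | 10 of 10 | 10 of 10 | 10 of 10 |
| SMPG rule, Visits 3 to 8 | 6 of 6 | 6 of 6 | 6 of 6 |

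**Step 3: confirm that the diary data would exist.** Protocol 9.2.2.3 asks for daily entries up to Visit 9 and for at least the week before each later visit, so a 7-day window is planned before all ten visits. Using nominal visit days (7 × week + 1) and diary Days 1 to 168, the on-site rule leaves all 168 virtual days unassigned. The days that fall in a usable 7-day window are 0 (virtual) and 4 × 7 = 28 (traditional). Under the SMPG rule they are 10 × 7 = 70 in each arm.

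**Step 4: look for a route round the gap.**
- Unscheduled on-site visits are for safety assessment only (Protocol Section 10), and SAP 2.5.5 says: "Unscheduled visit measurements are not included in the by-visit summaries".
- Visit 13 can be on-site if there is an adverse event (Protocol 10.1.6), but it follows treatment.
- After premature discontinuation, "end of treatment assessments will be re-allocated to the next scheduled visit for the patient". This could place some doses for early discontinuers, but not for patients who stay on treatment.
- Doses are also documented in the e-CRF at visits (flow chart; Protocol 10.1.3), but the SAP does not say that these feed the weekly mean.

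**Step 5: companion slips.**
- SAP 2.1.3.4 averages fasting SMPG over the 7 days before each on-site visit. Of the four corresponding post-baseline visits, that gives 4 of 4 in the traditional arm and 0 of 4 in the virtual arm.
- The first block of Table 2 in SAP 2.5.4 lists OSES Part 1, which also has its own by-visit block, and OSEP Part 1 appears nowhere in the table. OSEP Part 1 is planned at baseline and Week 24 (SAP 2.1.7.3), so 0 of its 2 time points have a stated window. OSES Part 1 has two Week 24 windows (141 to 196 and 155 to 196); the wider one overlaps its Week 20 window (127 to 154) on Days 141 to 154.

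**The case against.** The strongest reply is that the dose statistic carries its own date-based definition. Sections 2.4.3.2 and 2.5.3 both take the doses in the week before the visit, at each visit, with no on-site limit, and a programmer could compute that in both arms. On this view the SAP contradicts itself rather than prescribing an empty column, and 0 of 10 is the result only if 2.5.4 prevails. That is fair as far as it goes. But 2.4.3.2 names 2.5.4 as the process for assigning visits, so following the rule is the more direct reading, and two sections that yield different tables need reconciling in any case.

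On-site might also be shorthand for Visits 6, 8, 10 and 12 in both groups, since the virtual group has corresponding visits and post-baseline body weight for U/kg is scheduled only then. Section 2.5.4 itself separates visit modes for SMPG and PROs, which tells against this. Even if it were accepted, Visits 3, 4, 5, 7, 9 and 11 would still have no diary-based dose in either arm. The weight argument does not force it: 2.5.3 carries the last weight forward.

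The point about consequences stands. e-CRF doses exist in both arms, only the diary-based weekly mean is affected, no dose model or between-arm test was planned, and SAP Section 2 limits the output to basic descriptive tables or listings for 15 randomized patients. Descriptive by-visit dose tables remain possible under that limit, so the point is not moot. The fasting SMPG endpoint is exploratory, and the Table 2 label is an evident slip; both are minor.

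**Conclusion.** The concern holds. As written, the rule gives the virtual arm a diary-based weekly mean dose at 0 of 10 treatment visits and the traditional arm at 4 of 10, with no visit in common, against a stated plan to report at each visit. The counts rest on the literal text of 2.5.4 and the scheduled visit modes; the day counts also assume nominal visit dates, but the visit counts do not depend on them. This should be corrected before the dose tables are programmed. It is an error in the derivation, not a loss of data, and it touches no primary or safety conclusion.

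**What to change.** - **SAP 2.5.4, insulin doses:** adopt the SMPG rule. Assign each dose to the next visit the patient actually performs after data collection, whatever its mode (on-site, phone or virtual), from Visit 3 to Visit 12 or Visit 700. This also keeps premature end-of-treatment visits, which 2.5.4 then re-allocates.
- **Visit 700:** define it in one line. The SAP does not; it is read here, from context, as the premature end-of-treatment visit.
- **SAP 2.1.3.4:** replace the on-site wording with Visits 6, 8, 10 and 12 in both groups, on-site or the corresponding virtual visit.
- **SAP 2.5.4, Table 2, first block:** change OSES Part 1 to OSEP Part 1. This gives OSEP Part 1 its baseline and Week 24 windows and removes the duplicate OSES window.
- **SAP 2.4.3.2:** if doses will only be listed because 15 patients were randomized, say so there.

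Restricting dose summaries to Visits 6, 8, 10 and 12 in both groups would also align the arms, but the promise of a summary at each visit would then have to be amended and Visits 3 to 5 would stay empty.

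The cost is SAP wording only: two phrases, one table label and one definition, plus a sentence in 2.4.3.2 if doses are only to be listed. No new data are needed.
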